**The Rogosin Institute
[name]
[name]**

**An Open-Label, Phase II Efficacy Trial of the Implantation of
Mouse Renal Adenocarcinoma Cell-Containing Agarose-Agarose
Macrobeads in the Treatment of Patients with
Treatment-Resistant, Metastatic Pancreatic Adenocarcinoma or
Colorectal Cancer**

Clinical Study Protocol Number: 0911010739

IND Number: BB-IND 10091

**November 12th 2014
Amendment 11**

CONFIDENTIAL

This document and its contents are the property of and confidential to The Rogosin Institute. Any unauthorized copying or use of this document is prohibited.

SIGNATURE PAGE

THE ROGOSIN INSTITUTE APPROVAL PAGE

[figure not shown]
Protocol: An Open-Label, Phase II Efficacy Trial of the Implantation of Mouse Renal Adenocarcinoma Cell-Containing Agarose-Agarose Macrobeads in the Treatment of Patients with Treatment-Resistant, Metastatic Pancreatic Adenocarcinoma or Colorectal Cancer

Amendment: 11

Investigators' Agreement:

I have read the protocol and agree to conduct the study as outlined herein.

Signature:

Date:

3/17/17

Name (print):

[name].

PROTOCOL SYNOPSIS	
TITLE OF STUDY	An Open-Label, Phase II Efficacy Trial of the Implantation of Mouse Renal Adenocarcinoma Cell-Containing Agarose-Agarose Macrobeads in the Treatment of Patients with Treatment-Resistant, Metastatic Pancreatic Adenocarcinoma or Colorectal Cancer
Investigators/ Study Centers:	[name] [name] Weill Cornell Medicine/The Rogosin Institute [name]. [name]
Objectives:	
The primary efficacy outcome for colorectal cancer is post-implantation all-cause mortality, where time to death is defined as the time from the first scan showing disease progression after completion of prior treatment (time of origin, T₀) to death from any cause.
 
The primary objective for pancreatic cancer is to determine the Response Rate (RR), at 2 weeks, 4 weeks, 8 weeks, 3 months, 6 months, 9 months, 12 months or longer as possible, of subjects treated with macrobeads after they have failed standard chemotherapeutic regimens or have decided not to pursue standard or experimental chemotherapy for treatment-resistant, metastatic pancreatic adenocarcinoma.
 
The secondary objectives for both pancreatic and colorectal cancer are outlined in Section 3 of this protocol.

Rationale for Dosage:	Based on the animal studies conducted to date, as well as the Phase I human trial that has enrolled 31 subjects to date, a reasonable dosage range (number of beads to be implanted) is 8 macrobeads per kilogram of body weight. We know that 16 macrobeads per kilogram were also well-tolerated in the Phase I human trial, but, at least with a single dose, this number was not seen to be any more effective than 8 macrobeads per kilogram. As it is planned to carry out up to four implants (over approximately 12 months) in this Phase II trial, each implantation will be carried out at the 8 macrobeads per kilogram dosage.
Study Design:	
This is an open-label clinical trial. The clinical trial will have duration of 12 months and involve a potential total of four macrobead implants, each no less than three months apart. A total of 74 subjects will be treated. After the formal phase of the trial is completed, subjects will be followed for life.
 
The response of each subject to the intraperitoneal implantation of the RENCA agarose-agarose macrobeads will be measured as outlined in Section 3 of this protocol.
 
Each implant will be considered as Day 0. Post implant follow-up visits will be done in reference to the corresponding Implantations i.e. Days 14, 30, 60 and 90. Because much of the testing will be objective in terms of

PROTOCOL SYNOPSIS	
	quantifiable clinical laboratory, bias on the part of subjects, investigators, and analysts should be minimized.
Planned Sample Size:	The study will enroll a total of 116 evaluable subjects with advanced pancreatic cancer and colorectal cancer, and implant 74 eligible patients. An evaluable subject is defined as a subject who completes the first implantation of the RENCA agarose-agarose macrobeads. If a subject signs an Informed Consent and is not implanted, the subjects will not be classified as evaluable and will be replaced. These subjects will be classified as screen failures
Inclusion Criteria:	
 1. Histologically-confirmed adenocarcinoma of the pancreas, colon, or rectum. 2. Radiographic evidence of metastatic cancer of the colon or rectum. 3. The subject has pancreatic cancer that is unresectable or already metastatic or colorectal cancer that has failed available treatment modalities. 4. For the pancreas subjects, he/she may be accepted without prior chemotherapy or with multiple therapies that have failed. The colon and rectal cancer subjects must have failed available chemotherapy/targeted regimens. There is no limit to the number of prior chemotherapeutic regimens. 5. The subject must have evidence of progressive disease defined as at least one of the following: 
 a. Progressive measurable disease: using conventional solid tumor criteria b. Increasing tumor markers and/or activity on PET-CT SUV measurement 6. All clinically significant toxic effects (excluding alopecia) of prior surgery, radiotherapy, or hormonal therapy have resolved to \leq Grade 1 based on the NCI-CTCAE v 3.0, with the exception of peripheral neuropathy, which must have resolved to Grade \leq 2. 7. The subject has an Eastern Cooperative Oncology Group performance status (ECOG PS) of 0-2. 8. The subject has adequate hematologic function (minimum requirements: absolute neutrophil count [ANC] \geq 1500/mL, hemoglobin \geq 9 g/dL, and platelets \geq 100,000/mL). 9. The subject has adequate hepatic function (bilirubin \leq 1.5 times the upper limit of normal (ULN)), aspartate transaminase [AST] and alanine transaminase [ALT] \leq 3 times the ULN, or \leq 5 times the ULN, if liver metastases are present). 10. The subject has adequate renal function (creatinine \leq 2.0 mg/dL). 11. The subject has adequate coagulation function (an international normalized ratio [INR] \leq 1.5 and a partial thromboplastin time [PTT] \leq 5 seconds above the ULN [unless on oral anticoagulant therapy]). Subjects receiving full-dose anticoagulation therapy are eligible provided they meet all other criteria, are on a stable dose of oral anticoagulant or low molecular weight heparin (and if on warfarin have

PROTOCOL SYNOPSIS	
	
a therapeutic INR between 2 and 3).
 
 12. The subject has a life expectancy of 6 weeks. 13. The subject is male or female and at least 18 years of age. For females, a negative pregnancy test is required. 14. The subject agrees to use contraceptives while on study, if sexually active. 15. The subject has provided signed informed consent.
Exclusion Criteria:	
 1. Any condition (cardiovascular or other), making subject an unacceptably high anesthetic or surgical risk based on current anesthesia/general surgery standards. 2. Positive testing for HIV. 3. Cognitive impairment sufficient to render the subject incapable of giving informed consent. 4. Hypersensitivity reaction that, in the opinion of the investigators, poses an increased risk of an allergy to the macrobeads, particularly any known allergy to murine antigens or body tissues. 5. Surgical treatment or chemotherapy within three weeks of scheduled macrobead implantation or within four weeks of bevacizumab (or similar drugs), or radiation therapy within four weeks of scheduled macrobead implantation. 6. Investigational medications for their respective tumors within one month of baseline evaluation. 7. The subject has inadequate hematologic function (absolute neutrophil count [ANC] < 1500/mL, hemoglobin < 9 g/dL, and platelets < 100,000/mL). 8. The subject has inadequate hepatic function [bilirubin > 1.5 times the upper limit of normal (ULN)], aspartate transaminase [AST] and alanine transaminase [ALT] > 3 times the ULN, or > 5 times the ULN, if liver metastases are present). 9. The subject has inadequate renal function (serum creatinine > 2.0 mg/dL). 10. The subject has inadequate coagulation function (an international normalized ratio [INR] > 1.5 and a partial thromboplastin time [PTT] > 5 seconds above the ULN [unless on oral anticoagulant therapy]). Subjects receiving full-dose anticoagulation therapy are eligible provided they meet all other criteria, are on a stable dose of oral anticoagulant or low molecular weight heparin (and if on warfarin have a therapeutic INR between 2 and 3). 11. Hepatic blood flow abnormalities: portal vein hypertension and thrombosis; and/or large volume of ascites. 12. Concurrent cancer of any other type except skin cancer (excluding melanoma). 13. History of allergic reactions to mouse antigen. 14. The subject has an ongoing or active infection, symptomatic congestive heart failure, unstable angina pectoris, serious cardiac

PROTOCOL SYNOPSIS	
	
arrhythmias, (well-controlled atrial fibrillation, is permitted,) psychiatric illness/social situations that could interfere with the subject's ability to participate in the protocol, active bleeding.
 
15. As a result of the medical history, examination or blood testing, the investigator considers the subject unfit for the study.

Efficacy Variables:	
The response of each subject to the intraperitoneal implantation of the RENCA agarose-agarose macrobeads will be measured after each implantation with respect to changes in:
 
 • Primary tumor size • Size or number of secondary/metastatic tumors • Tumor marker (such as CEA, CA 19-9 and CA-125) or other relevant biochemical parameters such as liver enzymes, alkaline phosphatase, lactic dehydrogenase • Cellular and humoral immune status • Global clinical status or rating • Activities of daily living (ADL) rating • Symptom rating/severity (including narcotic analgesic consumption' visual analog pain scale; • Quality of life- EORTC • ECOG and Karnofsky Performance Status • Abdominal MRI/PET/CT scan with other imaging studies as appropriate for the subject's tumor type (primary and metastatic) and condition
Safety Variables:	
The following safety variables will be monitored to insure the safety of the participants in the study:
 
 • Complete physical examination with all vital signs • Weight • Global Clinical Assessment • EKG • Biochemical profile including appropriate tumor markers • Amylase, lipase • Complete blood count (CBC) with differential WBC • Erythrocyte sedimentation rate • C-reactive protein • Standard biochemical profile • Liver function (AST, ALT, LD, alkaline phosphatase, GGT) • Tumor markers as appropriate and available • Urinalysis • Coagulation profile (PT, INR, PTT) • Hepatitis B, C, E • HIV • Immunoglobulin levels (IgA, IgG, IgE, IgM) • Skin testing with murine epithelial antigen preparation, with positive

PROTOCOL SYNOPSIS	
	
and negative controls
 
 • Cellular and humoral immune function 
 ○ T cells ○ Cytokine production ○ B cells ○ Antibodies to common bacteria and viruses (such as diphtheria, tetanus, mumps, rubella) ○ Quantitative IgG subclass determinations ○ NK cells count (CD16) 
Analysis of circulating tumor cells.
 
 • Ecotropic murine leukemia virus (e-MuLV) (PCR-based assay) • Ultrasound examination, if medically indicated, will include views of the hepatic veins and inferior vena cava to be certain that they are free of clots and that there is free peritoneal drainage
Principles of Statistical Analysis:	
The critical parameters of this Phase II trial are those related to efficacy and safety. Various markers, such as CEA, CA 19-9, CA125 and C-reactive protein, amylase, liver function tests, cell counts, and cytokine levels, will be sampled and analyzed in relationship to their baseline values.
 
Given the study design, simple population comparisons designed for small samples (non-normal distribution) as well as simple trend analysis for selected parameters will be performed. The data from all subjects, including those who withdraw or are withdrawn from the study will be analyzed. All data will be analyzed using SAS software.

TABLE OF CONTENTS

1	LIST OF ABBREVIATIONS	11
2	BACKGROUND	13
3	OBJECTIVES	18
3.1	Objectives for the advanced colorectal cancer	18
3.1.1	Efficacy.....	18
3.1.2	Safety	19
3.1.3	Exploratory	19
3.2	Objectives for the advanced pancreatic cancer	19
3.2.1	Primary Objective.....	19
3.2.2	Secondary Objectives	20
3.2.3	Exploratory objectives	21
3.3	Rationale for Study Dosages	21
4	INVESTIGATIONAL PLAN	22
4.1	Description of Overall Study Design and Plan	22
4.2	Study Device/Biological Product	23
4.3	Selection of Study Population	25
4.3.1	Inclusion Criteria:.....	25
4.3.2	Exclusion Criteria:.....	26
4.4	Screening to Exclude Subjects with Allergic Reactions to Mouse Antigens	27
4.5	Treatments	27
4.5.1	Dosage Determination	27
4.5.2	Drug Labeling.....	27
4.6	Assessments	27
5	STUDY CONDUCT	29
5.1	Schedule of Assessments	29
5.1.1	Study Days -28 to -1:.....	29
5.1.2	Decision to Proceed with First Implantation	30
5.1.3	Study Day -28 to Study Day -1:	31
5.1.4	Visit 1 / Study Day 0:	31
5.1.5	Home Care:.....	31
5.1.6	Visit 2, Study Day 14 ± 3 days:.....	32

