4.6 Assessments

The objective of the proposed Phase II study of the RENCA macrobeads is, as stated above, to determine the human clinical efficacy of the cancer macrobeads in advanced pancreatic and colorectal cancer. Responses will be

assessed according to the usual categories of complete or partial response (with specification of percentage), and none/progression (with specification of percentage). Response assessment will be measured in terms of changes in volume of primary tumor and number of metastases as assessed by CT or MRI; tumor marker PSA, as well as the physician global clinical assessment; performance rating scale (Karnofsky or similar); quality of subject life as measured by the EORTC Quality of Life Scale. Alkaline phosphatase and lactic dehydrogenase will also be followed.

Other laboratory determinations to monitor subject response to the implantation of the macrobeads will include detection of inflammatory responses (CBC with differential WBC and platelet count, erythrocyte sedimentation rate, C-reactive protein, amylase, immunological changes, and cytokine production), RT-PCR (polymerase chain reaction) specific to e-MuLV DNA, plasma viremia, and antibodies to normal murine antigens.

A critical and unique addition to the endpoints for assessing efficacy will be, where possible, a careful search for and identification of the niches of cancer stem and other cells within the niche bodies of the tumors the macrobeads are being used to treat. Markers of the niche bodies used to identify them and study their state (numbers, integrity of surround blood vessels, degree of stress) will include HLA, CD44+, CD133+, p27, Ki67, and the Tunel assay for apoptosis. Determination of the presence or absence of circulating tumor cells will also be made. When possible/available, pathology specimens will be examined for cancer stem cell niches.

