5.6 Clinical Laboratory Parameters

The following clinical laboratory parameters will be tested in all subjects (the schedule is summary in Appendix 2 – Section 9.2):

- EKG
- Biochemical/immune system profile including
- Complete blood count (CBC) with differential WBC and platelet count
- Erythrocyte sedimentation rate
- C-reactive protein
- Biochemical profile as outlined above with amylase, lipase at screening, and thereafter as medically necessary
- Liver function (AST, ALT, LD, alkaline phosphatase, GGT)
- Urinalysis
- Coagulation profile (PT, INR, PTT)

- Hepatitis B, C, E
- HIV
- CEA, CA 19-9, CA 125
- Immunoglobulin levels (IgA, IgG, IgE, IgM)
- Skin testing with murine epithelial antigen preparation, along with positive and negative controls
- Cellular immune function
 - T cells
 - Cytokine production
 - B cells
 - Antibodies to common bacteria and viruses (diphtheria, pertussis, tetanus, mumps, rubella)
 - Quantitative IgG subclass determinations
 - NK cells count (CD16)
- Ecotropic murine leukemia virus (e-MuLV) (PCR-based assay)
- Abdominal/whole body MRI/CT scan with other imaging studies as appropriate for the subject's tumor (primary and metastatic) and condition. Ultrasound examination, if medically indicated, will include views of the hepatic veins and inferior vena cava to be certain that they are free of clots and that there is free peritoneal drainage.

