7 DATA MANAGEMENT AND STATISTICAL ANALYSIS

The critical parameters of this Phase II trial are those related to efficacy. Various markers, such as C-reactive protein, amylase, liver function tests, cell counts, and cytokine levels, will be sampled and analyzed. Given the study design, we will undertake simple population comparisons designed for small samples (non-normal distribution) as well as simple trend analysis for selected parameters. The data from all subjects, including those who withdraw or are withdrawn from the study will be analyzed. All data will be analyzed using SAS software.

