Murine Allergen Skin Test	X							X						X					X						
Positive and Negative Skin Test	X							X						X					X						
Circulating Tumor Cells	X			X			X			X			X			X			X			X			
Macrobuds Implantation (8 per kg body weight)		X						X						X					X						
Cefazolin (Prophylaxis – 1 gm)		X						X						X					X						
Chest X-Ray (PA / lateral)	X						X						X					X							

Implant	Screening	1					2					3					4					Follow-Up [12]	
		0	14	30	60	90	0	14	30	60	90	0	14	30	60	90	0	14	30	60	90	120	
Day	Visit	1	2	3	4	5	6	7	8	9	10	11	12	13	14	15	16	17	18	19	20	21	
CT Scan Chest (Non-Contrast) [11]	X																						
MRI of Abdomen [11]	X					X	X				X						X				X		X
MRI of Pelvis [11]	X					X	X				X						X				X		X
Tumor Mass Biopsy (where indicated)		X					X					X					X						
PET-CT Scan Whole Body	X						X				X						X				X		X [11]
Radionuclide Bone Scan [11]																							

1. Hematology Profile: WBC, RBC, hemoglobin, hematocrit, MCV, MCH, MCHC, RDW, platelets, automated differential WBC
2. Coagulation Panel: PT, PTT, INR
3. Comprehensive Metabolic Panel: CO₂, sodium, potassium, chloride, creatinine, BUN, calcium, total protein, albumin, total bilirubin, alkaline phosphatase, AST, ALT, glucose
4. GGT: gamma glutamyl-transpeptidase
5. Amylase and lipase are done at baseline, then as medically necessary for individual subjects
6. Hepatitis Panel: Hepatitis B, C and E
7. Serum pregnancy only for females of childbearing potential
8. Immunoglobulin Levels: IgA, IgG, IgE and IgM
9. Cytokine Panel: IL-6, TNF- α , TNF receptors p55, TNF receptors p75
10. Cellular Immune Function: T cells; B cells; antibodies to diphtheria, tetanus, mumps, rubella; quantitative IgG subclasses, NK cells count (CD16)
11. Only if clinically indicated.
12. Long-term follow-up will begin after the patient's EOS visit, and will continue for the duration of each subject's life, at 6-month intervals during the first 2 years of follow-up and then yearly thereafter. All examinations and treatment during this time will be guided by optimal patient care principles and the decisions of the physicians providing overall health care to the patient.

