6.2 Data Analysis

- All analyses will be done using SAS® version 9.1.3 or higher.
- All analyses will be exploratory. No confirmatory statistical testing will be done.
- Categorical variables will be summarized as frequencies and percentages in each category. In general, continuous variables will be summarized by numbers of patients, means, standard deviations, medians and ranges. The number of decimal places for minimums and maximums will be the same as the original data. The number of decimal places for means, medians and interquartile ranges will be the same as the original data plus one. The number of decimal places for measures of variance will be the same as the original data plus two.
- Laboratory data with qualifiers (e.g., "<") will be listed with but summarized without the qualifier.
- All p-values will be presented as illustrated below:

p-value	Presentation
≥ 0.01	2 decimal places
< 0.01 but ≥ 0.001	3 decimal places
< 0.001 but ≥ 0.0001	4 decimal places
< 0.0001	< 0.0001

- All analyses will be exploratory and, as such, there will be no significance level adjustments to control type I error.
- All statistical tests will be two-sided.
- Unscheduled data will not be summarized or analyzed (but will be listed, as noted above).

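### The Synopsis promises to analyse amylase against baseline, but amylase and lipase are scheduled only at screening and then when medically needed, so the comparison cannot be made for the treated population.

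*Protocol*

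**What the plan says.** **What is promised.** The Protocol Synopsis lists "Amylase, lipase" among its safety variables. Its paragraph on principles of statistical analysis says that "C-reactive protein, amylase, liver function tests, cell counts, and cytokine levels, will be sampled and analyzed in relationship to their baseline values". Protocol Section 7 says "Various markers, such as C-reactive protein, amylase, liver function tests, cell counts, and cytokine levels, will be sampled and analyzed", without mentioning baseline. Protocol Section 4.6 places "C-reactive protein, amylase, immunological changes, and cytokine production" among the laboratory tests used to follow the inflammatory response to the beads.

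**What is collected.** Protocol Section 5.6 provides "amylase, lipase at screening, and thereafter as medically necessary". Footnote 5 of the SAP schedule (Section 4) says "Amylase and lipase are done at baseline, then as medically necessary for individual subjects", and footnote 5 of Protocol Appendix 2 says the same. The SAP grid marks both tests at screening and nowhere else. The Section 5.1 lists for the follow-up visits name a metabolic panel with LD, GGT, CRP and direct bilirubin, but neither amylase nor lipase.

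**How off-schedule results are handled.** SAP Section 6.2 says "Unscheduled data will not be summarized or analyzed", though they are listed. SAP Section 6.1 has the same rule and gives repeat laboratory tests as an example. SAP Sections 6.4.2 and 6.4.4 define unscheduled by date: an observation or visit outside the nominal windows.

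**The concern.** A change-from-baseline analysis needs a baseline and a follow-up value from the same subjects. The plan gives every subject a baseline amylase, but a follow-up value only when a clinician has a reason to test. Later values will therefore be sparse and will come from subjects already suspected of a problem. A mean change computed from them would not describe the treated population.

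The beads lie free in the peritoneal cavity. Protocol Section 6.5.1 counts grade 3 or higher interference with intraperitoneal organ function as dose-limiting, and Section 3.2.2 makes tolerability for intraperitoneal organs a secondary objective in the pancreatic group, which is 40 of the 74 subjects to be implanted (Appendix 3, item 9). Enzyme rises in subjects with no reason to be tested would not be found. A reader of the final report who sees amylase named in the Synopsis as analysed against baseline could take the absence of a signal for more evidence than it is.

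**Working it through.** The plan states no figure on this point, so there is none to reproduce. The check is a count of scheduled tests and of days covered by the analysis windows.

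**1. Scheduled post-implant tests.**
- Follow-up visits (Protocol Section 5.1): Visits 2-5, 7-10, 12-15 and 17-21.
- Count: 4 + 4 + 4 + 5 = 17, that is, 4 implants x 4 visits (Days 14, 30, 60, 90) plus Day 120 after implant 4.
- Amylase or lipase in the Section 5.1 lists or marked in the SAP grid at these visits: 0 of 17.
- A subject with fewer than four implants has fewer visits; the numerator stays 0.

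The Protocol Appendix 2 grid is not used. In the text available, most of its laboratory rows carry a single mark, including tests that Section 5.1 repeats at nearly every visit, so marks were probably lost in conversion. Its footnote 5 is intact.

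**2. When an as-needed result counts as unscheduled.**
- SAP 6.4.4 windows: days 7-21, 23-37, 53-67 and 83-97 after each implant, plus 113-127 after implant 4. Each is 15 days.
- Implants 1 to 3, days 1-97: 4 x 15 = 60 days inside, 60/97 = 62%. Outside: 37/97 = 38%.
- Implant 4, days 1-127: 5 x 15 = 75 days inside, 75/127 = 59%. Outside: 52/127 = 41%.
- The protocol visit windows (Day 14 ± 3; Days 30, 60, 90 and 120 ± 5) are days 11-17, 25-35, 55-65, 85-95 and 115-125. All lie inside the SAP windows.

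An as-needed amylase drawn at an on-time visit therefore receives a nominal study day and could be summarised. One drawn between windows is listed only.

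**3. Baseline for later implants.** SAP 6.4.1.2 resets baseline before each implant to the latest available value. With no scheduled Day 90 test, the amylase baseline for implants 2 to 4 is either the screening value or one drawn because of a clinical concern.

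**4. Other routes into the report.**
- Protocol Section 6.1 makes clinically significant laboratory values adverse events, even without symptoms.
- SAP 11.1.2 summarises treatment-emergent adverse events.
- SAP 11.1.3 lists laboratory values of Grade 3 or higher or reported as adverse events, and sends all parameters to a spreadsheet with an out-of-range flag.
- SAP 11.1.3 summarises only a chosen subset of parameters, and amylase is not named in it.

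**The case against.** The strongest reply is that the SAP states that it supersedes the protocol's statistical considerations (Sections 1 and 13) and nowhere promises an amylase comparison. The Synopsis and Section 7 sentences would then be leftover wording. All analyses are exploratory (SAP 6.2), Section 4.6 treats amylase as an inflammatory marker, and no document ties a dose-limiting toxicity to amylase or lipase.

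Part of this stands. It limits the weight of the point, and a named pancreatic toxicity endpoint should not be read into the plan. But the superseding clause does not supply the missing measurements, and it does not touch Section 4.6 or the Synopsis list of safety variables. Nor does it settle how as-needed values are handled: the date-based definition admits an in-window result, while the repeat-test example in SAP 6.1 could be read to exclude it.

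A reader might go further and infer that there will be no post-implant amylase data at all, or that every as-needed result is barred from analysis. The documents support neither. Testing when medically needed is provided for, the results are listed, and exclusion from summaries turns on the date of the sample, not on whether the test was in the schedule.

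**Conclusion.** The contradiction holds. Amylase is promised as an analysed marker, against baseline in the Synopsis, but no systematic post-implant amylase or lipase is planned: 0 of up to 17 follow-up visits. The comparison cannot be made for the treated population. Existing values will be selected by indication, and those falling on about 38% to 41% of post-implant days will be left out of the laboratory summaries.

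The 38% to 41% is a share of days, not of results. It would equal the share of results only if as-needed samples fell evenly over time; samples taken at on-time visits would lower it. The denominators stop at day 97 after implants 1 to 3 and day 127 after implant 4. Any further days before the next implant also lie outside the windows.

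It would be too strong to say that an absence of pancreatic findings would be purely an artefact of the plan. Clinically significant values reach the adverse event tables and Grade 3 or higher values are listed. These routes work only when someone orders the test, so the gap is confined to rises in subjects who are not tested and to the laboratory summaries themselves.

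**What to change.** 1. Reconcile the Synopsis (safety variables and principles of analysis), Protocol Section 4.6 and Section 7 with Section 5.6, footnote 5 of both schedules and the SAP grid, so that the stated analysis matches what is collected. Either withdraw the baseline comparison or collect the data for it from samples already drawn. That choice is the sponsor's.
2. In either case, state in SAP 6.1, 6.2 and 11.1.3 that all post-implant amylase and lipase results, in or out of window, enter one table: worst post-implant CTCAE grade per subject, by cancer type.
3. Show number tested over number treated in that table, with a note that as-needed values are selected by indication. Without that denominator, bringing in these values could mislead as much as leaving them out.

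Cost: wording changes in the protocol and SAP and one more table. If the assays are scheduled, two tests are added to existing samples, with no new visit.
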